14.6 Appendix 6: Derived and Transformed Data

14.6.1 General

Multiple Measurements at One Time Point

- Mean of the measurements will be calculated and used in any derivation of summary statistics but if listed, all data will be presented.
- If there are two values within a time window (as per Section 14.3.1) the value closest to the target day for that window will be used. If values are the same distance from the target, then the mean will be taken.
- Participants having both High and Low values for Normal Ranges at any post-baseline visits for safety parameters will be counted in both the High and Low categories of "Any visit post-baseline" row of related summary tables. This will also be applicable to relevant Potential Clinical Importance summary tables.

Study Day

- Calculated as the number of days from First Dose Date:
 - Ref Date = Missing → Study Day = Missing
 - Ref Date < First Dose Date → Study Day = Ref Date First Dose Date
 - Ref Data ≥ First Dose Date → Study Day = Ref Date (First Dose Date) + 1

14.6.2 Study Population

Demographics

Age

- GSK standard IDSL algorithms will be used for calculating age where birth date will be imputed as follows:
 - Any participant with a missing day will have this imputed as day '15'.
 - Any participant with a missing date and month will have this imputed as '30th June'.
 - The age will be calculated by Data Management and mapped from ClinBase to SDTM dataset DM
- Birth date will be presented in listings as 'YYYY'.

Body Mass Index (BMI)

Calculated as Weight (kg) / [Height (m)]²

Treatment Compliance

Treatment compliance will be calculated based on the formula:

Treatment Compliance = Number of Actual Doses / (Planned Treatment Duration in Days * Frequency)

- Frequency is 2 for BID and 1 for QD. Treatment compliance could be greater than 100% if there are events of overdose. Cumulative compliance (since Day 1) at each visit will be calculated.
- Planned Treatment Duration is defined as 1 day for study part 1, and as 11 day for study part 2.

Extent of Exposure

- Number of days of exposure to study drug will be calculated based on the formula:
 Duration of Exposure in Days = Treatment Stop Date (Treatment Start Date) + 1
- Participants who were randomized but did not report a treatment start date will be categorised

Demographics

as having zero days of exposure.

• The cumulative dose will be based on the formula:

Cumulative Dose = Sum of (Number of Days x Total Daily Dose)

• If there are any treatment breaks during the study, exposure data will be adjusted accordingly.

14.6.3 Efficacy

Not applicable.

14.6.4 Safety

ECG Parameters

RR Interval

- IF RR interval (msec) is not provided directly, then RR can be derived as :
 - [1] If QTcB is machine read & QTcF is not provided, then:

$$RR = \left[\left(\frac{QT}{QTcB} \right)^2 \right] * 1000$$

[2] If QTcF is machine read and QTcB is not provided, then:

$$RR = \left[\left(\frac{QT}{QTcF} \right)^3 \right] * 1000$$

 If ECGs are manually read, the RR value preceding the measurement QT interval should be a collected value THEN do not derive.

Corrected QT Intervals

- When not entered directly in the eCRF, corrected QT intervals by Bazett's (QTcB) and Fredericia's (QTcF) formulas will be calculated, in msec, depending on the availability of other measurements.
- IF RR interval (msec) is provided then missing QTcB and/or QTcF will be derived as :

$$QTcB = \frac{QT}{\sqrt{\frac{RR}{1000}}}$$

$$QTcF = \frac{QT}{3\sqrt{\frac{RR}{1000}}}$$

Also QTc interval will be categorized as follows:

ECG Parameter	Potential Clinical Importance Range (PCI)	Units
Absolute QTc Interval	>450 to ≤480	msec
Absolute QTc Interval	>480 to ≤500	msec
Absolute QTc Interval	>500	msec
Increase from Baseline QTc	≤30	msec
Increase from Baseline QTc	>30 to ≤60	msec
Increase from Baseline QTc	>60	msec

Laboratory Parameters

• If a laboratory value which is expected to have a numeric value for summary purposes, has a non-detectable level reported in the database, where the numeric value is missing, but typically a character value starting with '<x' or '>x' (or indicated as less than x or greater than x in the comment field) is present, will be imputed with the value of the number without the sign for the descriptive statistics and the calculation of changes from baseline, e.g., a value of <2.2 will be imputed as 2.2 for the calculations. There will be no imputation in the data listings; all values will be displayed as recorded in the database.

14.6.5 Pharmacokinetic

Calculation of Pharmacokinetic Parameter Values Not Described in Section 9 (refer to GUI_51487 for pharmacokinetic analysis information)

lambda_z (terminal phase rate constant)

 Slope of the line determined by linear regression of logarithmically transformed concentration v. time data

%AUCex (percentage of AUC(0-∞) obtained by extrapolation)

Calculated as 100 x [AUC(0-∞) – AUC(0-t)] / AUC(0-∞)

14.6.6 Population Pharmacokinetic (PopPK)

Not applicable.

14.6.7 Pharmacodynamic

Not applicable.

14.7 Appendix 7: Reporting Standards for Missing Data

14.7.1 Premature Withdrawals

Element	Reporting Detail
General	Participant study completion (i.e. as specified in the protocol) was defined as participants who has received the study treatment per the protocol and who has completed all phases of the study including the follow-up visit. The study including the follow-up visit.
	The end of the study is defined as the last participant's last visit.
	Withdrawn participants will not be replaced in the study.
	All available data from participants who were withdrawn from the study will be listed and all available planned data will be included in summary tables and figures, unless otherwise specified.
	Withdrawal visits will be summarised as withdrawal visits.

14.7.2 Handling of Missing Data

Element	Reporting Detail
General	 Missing data occurs when any requested data is not provided, leading to blank fields on the collection instrument: These data will be indicated by the use of a "blank" in participant listing displays. Unless all data for a specific visit are missing in which case the data is excluded from the table. Answers such as "Not applicable" and "Not evaluable" are not considered to be missing data and should be displayed as such.
Outliers	Any participants excluded from the summaries and/or statistical analyses will be
Oddiers	documented along with the reason for exclusion in the clinical study report.

14.7.3 Handling of Missing and Partial Dates

Element	Reporting Detail
General	Partial dates will be displayed as captured in participant listing displays.
Adverse Events	 The eCRF allows for the possibility of partial dates (i.e., only month and year) to be recorded for AE start and end dates; that is, the day of the month may be missing. In such a case, the following conventions will be applied for calculating the time to onset and the duration of the event: Missing Start Day: First of the month will be used unless this is before the start date of study treatment; in this case the study treatment start date will be used and hence the event is considered On-treatment as per Appendix: Treatment States and Phases. Missing Stop Day: Last day of the month will be used, unless this is after the stop date of study treatment; in this case the study treatment stop date will be used. Completely missing start or end dates (i.e. no year specified) will remain

Element	Reporting Detail
	missing, with no imputation applied. Consequently, time to onset and duration of such events will be missing.
Element	Reporting Detail
Concomitant Medications/ Medical History	 imputed using the following convention: If the partial date is a start date, a '01' will be used for the day and 'Jan' will be used for the month If the partial date is a stop date, a '28/29/30/31' will be used for the day (dependent on the month and year) and 'Dec' will be used for the month.
	The recorded partial date will be displayed in listings.

14.8 Appendix 8: Values of Potential Clinical Importance

14.8.1 Laboratory Values

Division of AIDS (DAIDS, Version 2.0, November 2014) AE grades 2, 3, and 4 of lab abnormalities will be listed by subject, period/treatment, visit, and actual date and time.

Haematology				
Laboratory Parameter	Units	Category	Clinical Concern Range	
			Low Flag (< x)	High Flag (>x)
		Male		0.54
Hematocrit	Ratio of 1	Female		0.54
		Δ from BL	↓0.075	
	- //	Male		180
Hemoglobin	g/L	Female		180
		Δ from BL	↓25	
Lymphocytes	x109/ L		0.8	
Neutrophil Count	x109/ L		1.5	
Platelet Count	x109/ L		100	550
While Blood Cell Count (WBC)	x10 ⁹ / L		3	20

Clinical Chemistry				
Laboratory Parameter	Units	Category	Clinical Concern Range	
			Low Flag (< x)	High Flag (>x)
Albumin	g/L		30	
Calcium	mmol/L		2	2.75
Creatinine	μ mol/L	Δ from BL		↑ 44.2
Glucose	mmol/L		3	9
Magnesium	mmol/L		0.5	1.23
Phosphorus	mmol/L		0.8	1.6
Potassium	mmol/L		3	5.5
Sodium	mmol/L		130	150
Total CO2	mmol/L		18	32

Liver Function				
Test Analyte	Units	Category	Potential Clinical Importance Range	
ALT/SGPT	U/L	High	≥ 2x ULN	
AST/SGOT	U/L	High	≥ 2x ULN	
AlkPhos	U/L	High	≥ 2x ULN	
T Bilirubin	µmol/L	High	≥ 1.5xULN	
	µmol/L		1.5xULN T. Bilirubin	
T. Bilirubin + ALT		High	+	
	U/L		≥ 2x ULN ALT	

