- 7. Collect one troponin sample to be analyzed at local laboratory. A second sample will be collected, frozen and stored on site for potential high sensitivity troponin analysis.
- 8. 24-h Holter monitoring to be performed after confirming negative urine drug screen at screening, and must be within 30 days of Day 1. Holter monitoring on other days only if needed.
- 9. Plasma PK samples for bioanalysis for GSK2838232 will be collected pre-dose (within 15 minutes prior to dosing) and 0.5, 1, 1.5, 2, 2.5, 3, 3.5, 4, 6, 8, 12, 24, 36, 48, 72, 96, and 120 h post-dose. Samples will be acidified with an equal volume of 50 mmol citrate acid buffer pH 4.0.
- 10. An AE enquiry will be made at each visit, participants will be asked if they have experienced any neuropsychiatric adverse events, including psychosis or altered mental status. (see guidance for grading Altered Mental Status in Appendix 4).
- 11. Participants may be discharged after all study procedures are completed. Participants will be in house for PK blood samples on Day 3 (48 h), Day 4 (72 h), Day 5 (96 h) and Day 6 (120 h) of both study periods.

Table 3 Schedule of Assessments for Part 2: Repeated Doses for 11 days:

Management	Screening (within 30 days of Day 1 - carried out over	y															Follow- up		
Measurement	multiple days - except as noted in footnotes)	Day -1	Day 1	Day 2	Day 3	Day 4	Day 5	Day 6	Day 7	Day 8	Day 9	Day 10	Day 11 0 h	Day 12 24 h	Day 13 48 h	Day 14 72 h	Day 15 96 h	Day 16 120 h	7-14 days after last dose
Admission to Unit		Χ																	
Informed Consent	Х																		
Medical/medication/ drug/alcohol history (Demographics)	Х																		
Full Physical Examination	X													Х					
Brief Physical Examination		Х																	Х
Height, Weight, BMI	Х																		
Inclusion/Exclusion	Х																		
Medical History	Х																		
Vital Signs ¹	Х	Χ	Χ	Χ	Χ	Χ	Χ	Χ	Χ	Χ	Χ	Χ	Χ	Χ	Χ	Χ			Χ
12-lead ECG ²	Х	Χ	Χ	Χ	Χ		Х			Χ			X	Χ					Χ
Echocardiogram ³	Х																		
Drug/alcohol/ /cotinine Screen	Х	Х																	
HbsAg, HCV, HIV Testing	Х																		
Hem/Chem tests ⁴	Х	Χ		Х		Х		Х		Х			Х			Х			Х
Urinalysis	Х	Χ		Х		Х							Х			Х			Х
Serum FSH (as appropriate)	X																		
Troponin I ⁵	X	Χ	Х	Х			X			Χ			Х			Х			

Measurement	Screening (within 30 days of Day 1 - carried																		Follow- up

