3.3.1. Risk Assessment

Potential Risk of Clinical Summary of Data/Rationale for Risk Significance		Mitigation Strategy		
	Investigational Product (IP) GSK2838232			
Cardiovascular	Pre-clinical studies have shown the following findings: elevated heart rates, an isolated episode of non-sustained ventricular tachycardia and minimal to mild, sporadic troponin I elevations in dogs. A subsequent investigative cardiovascular study in telemetered dogs treated for four weeks did not replicate these effects. Isolated microscopic cardiovascular changes were noted (focal extramural arteritis and localized epicardial inflammation), however these changes were considered of uncertain relationship to GSK2838232 because similar findings occur at low incidence in normal beagles and there were no GSK2838232-related functional changes by telemetry and echocardiography, or changes in cTpnI and NTproBNP. In addition, there was no correlation between histologic changes and plasma exposure or heart tissue concentrations of GSK2838232. Toxicology studies in rat and dog (3, 6 and 9 months) did not demonstrate any evidence of cardiovascular injury or impact on cardiovascular function. In the four GSK2838232 studies conducted so far, there was no pattern of cardiovascular changes of clinical significance related to GSK2838232 and no	Participants will be clinically monitored for any signs of myocardial injury (chest pain, shortness of breath, pain with inspiration), elevated heart rate or arrhythmias. Samples for the assessment of troponin will be taken. Baseline ECG and Holter (to use for screening and for later comparisons if needed) Exposures of GSK2838232 will be closely monitored in the clinical study so as to not exceed PK stopping criteria.		

Potential Risk of Clinical Significance	Summary of Data/Rationale for Risk	Mitigation Strategy	
	clinically significant abnormality in electrocardiogram (ECG) values other than the two serious adverse events (SAEs) documented and discussed.		
	Review of published bevirimat preclinical and clinical safety data indicates no significant toxicities or adverse events (AEs) of interest, other than a 30% incidence of gastrointestinal symptoms (including diarrhea). There were no significant cardiovascular AEs reported in published clinical studies.		

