Cardiovascular	The RTV label includes the following cardiovascular AEs (which occurred in less than 2% of adult patients receiving RTV in all phase III/phase III studies and considered at least possibly related or of unknown relationship to treatment and of at least moderate intensity): cardiovascular disorder, cerebral ischemia, cerebral venous thrombosis, hypertension, hypotension, migraine, myocardial infarct, palpitation, peripheral vascular disorder, phlebitis, postural hypotension, tachycardia and vasospasm. During post-marketing use of RTV first-degree AV block, second-degree AV block, third-degree AV block, right	Participants will be closely monitored for any symptoms potentially associated with RTV administration. Specifically, participants will be clinically monitored for any signs of myocardial injury (chest pain, shortness of breath, pain with inspiration, cardiac troponin I [cTnI], ECG changes), elevated heart rate or arrhythmias. Serial ECGs will be used at each treatment period on-study.

Potential Risk of Clinical Significance	Summary of Data/Rationale for Risk	Mitigation Strategy	
	bundle branch block have been reported.		
Hepatitis	Hepatic transaminase elevations > 5 x the upper limit of normal, clinical hepatitis, jaundice, and hepatic dysfunction (including fatalities) have occurred in patients receiving RTV alone or in combination with other antiretroviral drugs. There may be an increased risk for transaminase elevations in patients with underlying hepatitis, pre-existing liver diseases, or liver enzyme abnormalities, and in patients taking multiple concomitant medications and/or with advanced acquired immunodeficiency syndrome (AIDS).	Enrolment into the study will be limited to healthy volunteers who do not have not underlying liver disease, hepatitis or liver enzyme abnormalities. Liver enzymes (ALT, AST, total and direct bilirubin, alkaline phosphatase) will be determined at screening and monitored throughout the study period.	
Pancreatitis	Pancreatitis has been observed in patients receiving RTV therapy, and in some cases fatalities have been observed.	Participants will be closely monitored for any symptoms of pancreatitis, including nausea, vomiting, abdominal pain and anorexia. Lipase will be monitored throughout the treatment period.	

Potential Risk of Clinical	Summary of Data/Rationale for Risk	Mitigation Strategy
Significance		

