6.2. Exclusion Criteria

A participant will not be eligible for inclusion in this study if any of the following criteria apply:

CONCURRENT CONDITIONS/MEDICAL HISTORY (INCLUDES LIVER FUNCTION AND QTc INTERVAL)

- 1. Alanine transaminase (ALT) >1.5x upper limit of normal (ULN)
- 2. Bilirubin >1.5xULN (isolated bilirubin >1.5xULN is acceptable if bilirubin is fractionated and direct bilirubin <35%).
- 3. Current or chronic history of liver disease, or known hepatic or biliary abnormalities.
- 4. Participants who have asthma or a history of asthma.
- 5. Medical history of cardiac arrhythmias or cardiac disease or a family or personal history of long QT syndrome.

CONCOMITANT MEDICATIONS

6. Unable to refrain from the use of prescription or non-prescription drugs, including vitamins, herbal and dietary supplements (including St John's Wort) within 7 days (or 14 days if the drug is a potential enzyme inducer) or 5 half-lives (whichever is longer) prior to the first dose of study medication, unless in the opinion of the Investigator and GSK Medical Monitor, the medication will not interfere with the study procedures or compromise participant safety.

RELEVANT HABITS

- 7. History of regular alcohol consumption (within 6 months prior to screening or unable to refrain from alcohol use from 5 days prior to admission through the last blood sample collected) defined as:
 - For US sites: an average weekly intake of >14 drinks for males or >7 drinks

- for females. One drink is equivalent to 12 g of alcohol: 12 ounces (360 mL) of beer, 5 ounces (150 mL) of wine or 1.5 ounces (45 mL) of 80 proof distilled spirits.
- 8. Regular use of tobacco- or nicotine- containing products within 6 months prior to screening. Unable to refrain from smoking from the Screening Visit through the last blood sample collected. As confirmed by a urine cotinine test.

CONTRAINDICATIONS

9. History of sensitivity to any of the study medications, or components thereof or a history of drug or other allergy that, in the opinion of the Investigator or Medical Monitor, contraindicates their participation.

DIAGNOSTIC ASSESSMENTS AND OTHER CRITERIA

- 10. Presence of hepatitis B surface antigen (HBsAg), or positive hepatitis C virus (HCV) test result at screening or within 3 months prior to first dose of study treatment.
- 11. Screening or baseline cardiac troponin I greater than the 99% cutoff (>0.045ng/ml by the Dimension Vista cTnI assay) for a given assay.

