Calcium (Ionized), High (mg/dL; mmol/L)	>ULN to < 6.0 >ULN to < 1.5	6.0 to <6.4 1.5 to < 1.6	6.4 to < 7.2 1.6 to < 1.8	≥ 7.2 ≥ 8

PARAMETER	GRADE 1 MILD	GRADE 2 MODERATE	GRADE 3 SEVERE	GRADE 4 POTENTIALLY LIFE- THREATENING
Calcium, Low (mg/dL; mmol/L) ≥ 7 days of age	7.8 to < 8.4 1.95 to < 2.10	7.0 to < 7.8 1.75 to < 1.95	6.1 to < 7.0 1.53 to < 1.75	< 6.1 < 1.53
<7 days of age	6.5 to < 7.5 1.63 to < 1.88	6.0 to < 6.5 1.50 to < 1.63	5.50 to < 6.0 1.38 to < 1.50	< 5.50 < 1.38
Calcium (Ionized), Low (mg/dL; mmol/L)	< LLN to 4.0 < LLN to 1.0	3.6 to < 4.0 0.9 to < 1.0	3.2 to < 3.6 0.8 to < 0.9	< 3.2 < 0.8
Cardiac Troponin I, High	Not applicable	Not applicable	Not applicable	Levels consistent with myocardial infarction or unstable angina as defined by the local laboratory
Creatine Kinase, High	3 to < 6 x ULN	6 to < 10 x ULN	10 to < 20 x ULN	≥ 20 x ULN
Creatinine, High	1.1 to 1.3 x ULN	> 1.3 to 1.8 x ULN OR Increase of > 0.3 mg/dL above baseline		≥ 3.5 x ULN OR Increase of ≥ 2.0 x above baseline

PARAMETER	GRADE 1 MILD	GRADE 2 MODERATE	GRADE 3 SEVERE	GRADE 4 POTENTIALLY LIFE- THREATENING
Creatinine Clearance 2 or eGFR, Low Report only one	Not applicable	< 90 to 60 mL/min or mL/min/1.73 m ² OR 10 to < 30% decrease from baseline	< 60 to 30 mL/min or mL/min/1.73 m ² OR ≥30 to <50% decrease from baseline	< 30 ml/min or mL/min/1.73 m ² OR ≥50% decrease from baseline or dialysis needed
Glucose (mg/dL; mmol/L) Fasting, High	110 to 125 6.11 to < 6.95	> 125 to 250 6.95 to < 13.89	> 250 to 500 13.89 to < 27.75	> 500 ≥ 27.75
Nonfasting, High	116 to 160 6.44 to < 8.89	> 160 to 250 8.89 to < 13.89	> 250 to 500 13.89 to < 27.75	> 500 ≥ 27.75
Glucose, Low $(mg/dL; mmol/L)$ $\geq 1 month of age$	55 to 64 3.05 to 3.55	40 to < 55 2.22 to < 3.05	30 to < 40 1.67 to < 2.22	< 30 < 1.67
<1 month of age	50 to 54 2.78 to 3.00	40 to < 50 2.22 to < 2.78	30 to < 40 1.67 to < 2.22	< 30 < 1.67
Lactate, High	ULN to < 2.0 x ULN without acidosis	≥ 2.0 x ULN without acidosis	Increased lactate with pH< 7.3 without life-	Increased lactate with pH< 7.3 with life-threatening consequences
Lipase, High	1.1 to < 1.5 x ULN	1.5 to < 3.0 x ULN	3.0 to < 5.0 x ULN	≥ 5.0 x ULN

PARAMETER	GRADE 1 MILD	GRADE 2 MODERATE	GRADE 3 SEVERE	GRADE 4 POTENTIALLY LIFE- THREATENING
Lipid Disorders (mg/dL; mmol/L) Cholesterol, Fasting, High ≥ 18 years of age	200 to < 240 5.18 to < 6.19	240 to < 300 6.19 to < 7.77	≥ 300 ≥ 7.77	Not applicable

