14.12.8 Safety Figures

Safety	Safety : Figures							
No.	Population	IDSL / TST ID / Example Shell	Title	Programming Notes	Deliverable [Priority]			
Labora	tory Values							
3.1.	Safety	As EG9	Plot of Selected Clinical Lab Tests Mean Change from Baseline by Treatment and Time – Part 1	Only include scheduled visits and for selected lab test (BNP, Tnp1, ALT, AST, Bili) Plots will be presented with treatment groups overlaid	SAC [1]			
3.2.	Safety	As EG9	Plot of Selected Clinical Lab Tests Mean Change from Baseline by Treatment and Time – Part 2	Only include scheduled visits and for selected lab test (BNP, Tnp1, ALT, AST, Bili) Plots will be presented with treatment groups overlaid	SAC [1]			
ECG				· · · · · · · · · · · · · · · · · · ·				
3.3.	Safety	EG9	Plot of Mean Change from Baseline QTcB and QTcF Data by Treatment and Time – Part 1	Plots will be presented with treatment groups overlaid	SAC [1]			
3.4.	Safety	EG9	Plot of Mean Change from Baseline QTcB and QTcF Data by Treatment and Time – Part 2	Plots will be presented with treatment groups overlaid	SAC [1]			
Vital Si	gns							
3.5.	Safety	As EG8	Box Plot of Change from Baseline for Vital Signs by Treatment and Time – Part 1	Plots will be presented with treatment groups overlaid	SAC [1]			
3.6.	Safety	As EG8	Box Plot of Change from Baseline for Vital Signs by Treatment and Time – Part 2	Plots will be presented with treatment groups overlaid	SAC [1]			

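### SAP 14.8.1 sets no troponin I criterion and DAIDS grades troponin only at Grade 4, so a smaller rise enters no clinical-importance or toxicity-grade table

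*SAP*

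**What the plan says.** **Why troponin is collected.** Protocol 3.3.1 records minimal to mild, sporadic troponin I elevations in dogs, which a later telemetry study did not replicate. The mitigation for the study drug includes: "Samples for the assessment of troponin will be taken". The ritonavir row names "cardiac troponin I [cTnI], ECG changes" among the signs of myocardial injury to be watched for.

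**When it is collected.** The schedules give troponin its own row, apart from haematology and chemistry. Part 1 samples at screening and Days -1, 1, 2 and 4. Part 2 samples at screening and Days -1, 1, 2, 5, 8, 11 and 14. The footnote in each reads "Collect one troponin sample to be analyzed at local laboratory", with a second sample frozen for possible high-sensitivity analysis.

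**The limit the protocol already uses.** Exclusion 11 covers "Screening or baseline cardiac troponin I greater than the 99% cutoff (>0.045ng/ml by the Dimension Vista cTnI assay".

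**How the SAP classifies laboratory values.** Section 14.8.1 gives limits for 19 analytes: 6 haematology, 9 chemistry and 4 liver. Troponin is not among them. For graded abnormalities it states that "Division of AIDS (DAIDS, Version 2.0, November 2014) AE grades 2, 3, and 4 of lab abnormalities will be listed by subject". In the DAIDS table (Protocol Appendix 4), Grades 1 to 3 do not apply to troponin I, and Grade 4 is "Levels consistent with myocardial infarction or unstable angina as defined by the local laboratory".

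**Where troponin is named.** Figures 3.1/3.2 plot mean change from baseline, with the note "Only include scheduled visits and for selected lab test (BNP, Tnp1, ALT, AST, Bili". The SAP addendum retitles them to show the mean with a 95% CI. It marks Tables 3.17/3.18 and 3.29/3.30 as unchanged.

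**The concern.** Safety is the first-listed primary objective of Part 2, where six participants receive active drug. In a group that small, useful safety information comes mostly from individual values crossing a limit set in advance. For troponin the analysis plan has no such limit short of the level linked to infarction or unstable angina. The threshold-based and grade-based tables could therefore show no troponin abnormality while a participant is above the level that would have kept them out of the study. Readers of the report would normally take an empty row or a missing entry in those tables as reassurance.

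**Working it through.** The plan states no figure on this point, so there is nothing to reproduce. The check has two parts.

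**1. Trace a post-dose value above 0.045 ng/mL but below Grade 4 through the planned displays.**

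| Display | Rule for entry | Value captured? |
|---|---|---|
| Tables 3.17/3.18 (worst case against PCI) | limit in SAP 14.8.1 | No: no troponin limit |
| Tables 3.29/3.30 (Grade 1 or higher) | DAIDS grade | No: Grades 1 to 3 do not exist for troponin |
| Listings 50/51 (participants with a PCI value) | limit in SAP 14.8.1 | Not triggered by this value alone |
| Listings 54/55 (Grade 2 or higher) | DAIDS grade | Not triggered by this value |
| Figures 3.1/3.2 | troponin is named | Only as part of a group mean |
| Tables 3.1/3.2 (all AEs) | investigator judges the change clinically relevant (Protocol 9.4.5, 12.5.1) | Depends on that judgement |
| Tables 3.19/3.20, Listings 46/47 (chemistry) | troponin handled as chemistry | Not stated in the SAP |

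On the last row the documents point both ways. Troponin has a separate schedule row and is absent from the chemistry panel in Protocol Appendix 2, and SAP 8.3 names no cardiac-marker category. Figures 3.1/3.2, however, place it beside ALT, AST and bilirubin as a clinical laboratory test.

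**2. Ask whether the mean plot with a 95% CI can stand in for a count.**

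Suppose one of n participants rises by x and the others do not change.

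- Mean change = x/n.
- Variance = (x² - x²/n)/(n - 1) = x²/n, so SD = x/√n.
- Standard error = SD/√n = x/n.
- Mean divided by standard error = 1, whatever the size of x.

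The 95% interval therefore always includes zero in this situation. The mean moves by x/6 in the Part 2 active group and by x/12 with 12 participants in Part 1.

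Assumed example (not trial data): n = 6, five participants stay at 0.02 ng/mL and one goes from 0.02 to 0.10.

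- Multiple of the cutoff: 0.10/0.045 = 2.2.
- Group mean after the rise: (5 × 0.02 + 0.10)/6 = 0.20/6 = 0.033 ng/mL, below 0.045.
- Mean change: 0.08/6 = 0.013.
- SD: 0.08/√6 = 0.0327. Standard error: 0.08/6 = 0.0133.
- 95% CI with t = 2.571 on 5 degrees of freedom: 0.013 ± 0.034, or -0.021 to 0.048.
- Participants counted under the current PCI criteria: 0/6. Participants above the cutoff: 1/6.

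The toxicity-grade count is also 0/6 if 0.10 ng/mL lies below the local laboratory's Grade 4 definition. The documents do not give that definition, so this is an assumption.

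**The case against.** The strongest reply is that troponin is not left unreported. A reader might infer that a sub-Grade-4 rise is counted in no safety table at all. The documents do not support that. Investigators must record clinically relevant laboratory changes as AEs, and those are counted in Tables 3.1/3.2. Listings 52/53 would show laboratory results identified as AEs if there are enough of them. If troponin is processed as chemistry, Tables 3.19/3.20 would summarise it, and Listings 46/47 would print every value and flag those out of range. All of this stands. What remains is that the AE route depends on individual judgement, the chemistry route is unstated, and a flag in a listing is not a count.

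It can also be said that the 95% CI added by the addendum makes a single case visible, because the bar widens. That is fair: with no change in anyone the interval would have no width. The wider bar still does not show who exceeded the cutoff, or that anyone did.

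Three further inferences should be resisted.

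- Troponin elevation is not established as the leading risk. The later dog study showed no troponin change, and Protocol 3.3.3 concludes that cardiac toxicity is unlikely.
- Magnesium, phosphorus and total CO2 have PCI limits, and BNP is in the figures, although none is in Appendix 2 or the schedules. A criterion without data counts nobody, and these entries do not cause the troponin gap. Nor do the documents prove that they are never measured: troponin itself is absent from Appendix 2, and the laboratory manual is not available.
- The lack of a PCI limit for lipase is not a gap, because DAIDS grades lipase from 1 to 4 and elevations reach Tables 3.29/3.30.

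Finally, the study is descriptive and tests no hypotheses, and reusing an entry cutoff as a reporting limit is a choice. That limits the weight of the point but does not remove it.

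**Conclusion.** The concern holds in a limited form. No PCI or toxicity-grade table counts a troponin I rise above the protocol's own cutoff but below Grade 4, and such a rise does not by itself trigger Listings 50/51 or 54/55. It would appear in the group mean-change figures, in the AE tables if the investigator judges it clinically relevant, and possibly in the chemistry outputs.

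The size is one participant in six going uncounted by the PCI criteria in the assumed Part 2 example. The trace of displays rests only on the SAP and protocol text. The numerical example rests on assumed concentrations, and its toxicity-grade part also rests on the unknown local Grade 4 definition. No planned estimate is biased. This is a worthwhile, inexpensive improvement to how a primary safety objective is reported.

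**What to change.** In SAP 14.8.1, add a reporting criterion for troponin I: above the 99th-percentile cutoff of the assay used, which is 0.045 ng/mL for the assay named in exclusion 11. Then:

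- count participants above it by treatment in Tables 3.17/3.18;
- include them in Listings 50/51;
- show individual troponin profiles with the cutoff line alongside the mean plot in Figures 3.1/3.2;
- state that troponin is analysed with chemistry, so that Tables 3.19/3.20 and Listings 46/47 clearly include it.

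The addendum documents changes made after database lock. If this addition is also made after lock, it should be labelled as such. It affects reporting only and sets no rule for managing participants.

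The cost is a few extra lines of programming; the samples are already scheduled. The downside is that an isolated minor exceedance may be flagged. Removing BNP, magnesium, phosphorus and total CO2, or documenting where they are measured, is optional tidying that changes no result.
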